#### 5.4.2. Examination of Subgroups

The list of subgroups may be used in descriptive summaries and statistical analyses. Additional subgroups of clinical interest may also be considered. The following subgroup analyses will only be performed at final analysis unless otherwise specified.

- If the percentage of subjects is small within a particular subgroup, then the subgroup categories may be refined prior to unblinding the trial.
- If the category cannot be refined further, then descriptive rather than statistical comparisons may be performed for the particular subgroup.

Subgroup	Categories	Timing	Motivation
Any advanced therapy experience	Advanced therapy naïve vs. Advanced therapy experienced	Interims, SAC	Prior expectation of clinical importance

#### 5.5. Multiple Comparisons and Multiplicity

In general, no multiplicity adjustments will be made however for relevant data types standard analysis methods that correct for multiplicity may be employed, for example in the analysis of exploratory transcriptomic data.

#### 5.6. Other Considerations for Data Analyses and Data Handling Conventions

Other considerations for data analyses and data handling conventions are outlined in the following appendices:

Section	Component
15.3	Appendix 3 : Assessment Windows
15.4	Appendix 4 : Treatment Phases and Study Phases Study Phases and Treatment Emergent Adverse Events
15.5	Appendix 5 : Data Display Standards & Handling Conventions
15.6	Appendix 6 : Derived and Transformed Data
15.7	Appendix 7 : Reporting Standards for Missing Data
15.8	Appendix 8 : Values of Potential Clinical Importance

## 6. STUDY POPULATION ANALYSES

### 6.1. Overview of Planned Study Population Analyses

The induction study population analyses will be based on the “Screened” and “Enrolled” populations, unless otherwise specified.

Population outputs will be generated for the participants in the four study phases illustrated in [Figure 1](#) Participant Flow:

- Group A: Induction Phase
- Group B: Extended Treatment Phase (Week 10 Responders)
- Group C: Open Label Induction (Week 10 Non-Responders)
- Group D: Open Label ETP (Week 22 Responders)

This pattern will continue for all reported domains in this study.

Study population analyses including analyses of subject’s disposition, protocol deviations, demographic and baseline characteristics, prior and concomitant medications, and exposure and treatment compliance will be based on GSK Core Data Standards. Details of the planned displays are presented in [Appendix 12](#): List of Data Displays.

## 7. SAFETY ANALYSES

All safety evaluations will be based on the safety population. Displays of adverse events, laboratory values, ECG and vital signs will be generated. These data will be clinically interpreted based on a number of factors, including taking account the investigator-reported relationships of either adverse events or laboratory abnormalities to investigational product.

Safety endpoints of all types will be reported by study phase (Induction phase, Extended Treatment Phase, Open Label Induction Phase, Open Label Extended Treatment Phase). All study phases will use the same pre-dose baseline. The details of planned displays are provided in [Appendix 12: List of Data Displays](#).

No formal statistical testing will be performed on safety data.

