- 1 Unless specified otherwise, all samples will be taken prior to administration of study treatment.
- 2 A highly sensitive urine pregnancy test is adequate. If a urine test cannot be confirmed as negative, a serum pregnancy test is required.
- 3 See Section 6.2, for details of dosing durations and monitoring periods.
- 4 IBDQ, FACIT-Fatigue, SF-36, PGIC and PGIS are to be performed before any other assessments on visit days.
- 5 Vital signs to be taken every 30 minutes (± 5 minutes) until completion of post dose monitoring period. For participants who have discontinued treatment but remain on study, post-dose monitoring does not apply.
- 6 Additional PK sample immediately after end of IV infusion (preferably within 15 minutes of end of IV infusion).
- 7 In case of Early treatment discontinuation, or study withdrawal, the investigator should undertake a Follow-Up visit approximately 16 weeks after the last dose event to allow safety monitoring following drug washout.
- 8 Participants who discontinue study treatment are encouraged to complete remaining scheduled visits for the treatment phase they are in. However, an Early withdrawal visit is only required for participants who prematurely discontinue study treatment and do not agree to complete the remaining scheduled visits for that phase.
- 9 A single ECG to be taken any time within post-dose monitoring period
- 10 Faecal Calprotectin sample may be taken up to 48 hours prior to scheduled visit.
- 11 Exit interview, if applicable, to be undertaken either at Early Withdrawal or Follow-Up.
- 12 Home health care / telemedicine visits may be permitted where applicable country and local regulations and infrastructure allow.
- 13 Complete 4-domain Mayo Score (including Endoscopy) to be performed if withdrawal from study treatment occurs after Week 16 but prior to Week 22 (all participants). The endoscopy is to be performed either at the Early Withdrawal Visit (for participants who do not wish to complete remaining scheduled visits), or at Week 22 (for participants that agree to complete remaining scheduled visits after withdrawing from treatment).

- Safety, pharmacokinetic, pharmacodynamic/biomarker and/or other assessments may be altered during the study based on newly available data (e.g. to obtain data closer to the time of peak plasma concentrations) to ensure appropriate monitoring.

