4.2. Scientific Rationale for Study Design

This is the first study of GSK2831781 in participants with moderate to severe active UC, and the first repeat dose study. There are two primary objectives, the first of which is to evaluate the safety and tolerability of repeat doses GSK2831781. The second primary objective is to characterise the efficacy dose-response in the Induction Phase of GSK2831781 in patients with moderate to severe active UC.

The placebo group is required for a valid evaluation of adverse events attributable to GSK2831781 treatment versus those independent of GSK2831781 treatment. The placebo participants will also serve as controls for the biomarker and efficacy assessments. Participants randomised to receive placebo during the Induction Phase who have not responded by the Induction Assessment (Week 10) will have opportunity to access Open Label treatment with GSK2831781 450 mg IV.

The endpoint chosen for primary characterisation of the dose-response is the change from baseline in Mayo score (See Appendix 7, Section 10.7) at Week 10. This will be evaluated alongside the key secondary endpoint of endoscopic mucosal healing. Longitudinal data demonstrate that patients who attain mucosal healing have a superior long-term prognosis, including lower risk of future surgery and hospitalisation, need for systemic steroids, and development of colorectal cancer [Rutter, 2004]. Patient-reported outcomes are also included in the secondary and exploratory analyses.

In addition to endoscopic and symptomatic assessments, other key endpoints contributing to an understanding of whether GSK2831781 successfully ameliorates mucosal inflammation are being undertaken, including: histological, immunohistochemical and transcriptomic assessment of gut biopsies; levels of faecal calprotectin; and C-reactive protein (CRP) concentrations in blood. Further exploratory endpoints include characterisation of PK and efficacy with a single dose level of subcutaneous GSK2831781 in the Extended Treatment Phase, to determine applicability of this dosing route in future studies.

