### 5.2. Baseline Definitions

The baseline value will be the latest pre-dose assessment with a non-missing value, including those from screening and unscheduled visits

If baseline data is missing no derivation will be performed and baseline will be set to missing.

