#### **Assessment windows do not cross study phases**

An exception to the general rule of allocating observations to the nearest visit concerns the transition between study phases. Assessment windows should not allocate a visit to a study phase until the study phase begins for that participant (i.e. the Study Day that they receive their first dose for that study phase).

For example, even if an Unscheduled visit on Week 13 for a responding participant is closest to the first visit for the Extended Treatment Phase, the observations from the Unscheduled visit would be allocated to the Induction Phase because the Extended Treatment Phase has not started.

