211* (First dose of Period + 113)	198* (First dose of Period + 100)	225* (First dose of Period + 127)	WEEK 30
85* (First Dose of Period + 1)	Participant's first dose of OL	92* (First dose of Period + 8)	OL WEEK 12
99* (First dose of Period + 15)	93* (First dose of Period + 9)	113* (First dose of Period + 29)	OL WEEK 14
127* (First dose of Period + 43)	114* (First dose of Period + 30)	141* (First dose of Period + 57)	OL WEEK 18
155* (First dose of Period + 71)	142* (First dose of Period + 58)	A day prior to participant's first dose of OL ETP. For participants who do not take a subsequent dose, maximum of 'OL Week 22 dosing date +3' and day 197	OL WEEK 22
183* (First Dose of Period + 1)	Participant's first dose of OL ETP	186* (First dose of Period + 4)	OL WEEK 26
211* (First dose of Period + 29)	187* (First dose of Period + 5)	225* (First dose of Period + 43)	OL WEEK 30
239* (First dose of Period + 57)	226* (First dose of Period + 44)	253* (First dose of Period + 71)	OL WEEK 34
267* (First dose of Period + 85)	254* (First dose of Period + 72)	281* (First dose of Period + 99)	OL WEEK 38
295* (First dose of Period + 113)	282* (First dose of Period + 100)	309* (First dose of Period + 127)	OL WEEK 42
* For delayed first dose in the study phase : - If the first dose of a study phase is within the first visit window of that study phase, then use the number outside brackets in each subsequent window. - If the first dose of a study phase is post-ending timepoint of the first visit window of that study phase, then use the bracketed derivation in each subsequent window.			

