3.30.	Safety OL ETP	LB1	As above for Open Label Extended Treatment Phase	Rationale: ICH E3	SAC
3.31.	Safety	LB17	Summary of Worst-Case Chemistry Results by PCI Criteria Post-Baseline Relative to Baseline for Induction Phase	Rationale: ICH E3 and disclosure	SAC
3.32.	Safety ETP	LB17	Summary of Worst-Case Chemistry Results by PCI Criteria Post-Baseline Relative to Baseline for Extended Treatment Phase	Rationale: ICH E3 Footnote: "Note: Induction phase baseline used"	SAC
3.33.	Safety OL I	LB17	Summary of Worst-Case Chemistry Results by PCI Criteria Post-Baseline Relative to Baseline for Open Label Induction Phase	Rationale: ICH E3 Footnote: "Note: Induction phase baseline used"	SAC
3.34.	Safety OL ETP	LB17	Summary of Worst-Case Chemistry Results by PCI Criteria Post-Baseline Relative to Baseline for Open Label Extended Treatment Phase	Rationale: ICH E3 Footnote: "Note: Induction phase baseline used"	SAC
Laboratory: Haematology					
3.35.	Safety	LB1	Summary of Haematology Changes from Baseline for Induction Phase	Rationale: ICH E3	SAC
3.36.	Safety ETP	LB1	As above for Extended Treatment Phase	Rationale: ICH E3	SAC
3.37.	Safety OL I	LB1	As above for Open Label Induction Phase	Rationale: ICH E3	SAC
3.38.	Safety OL ETP	LB1	As above for Open Label Extended Treatment Phase	Rationale: ICH E3	SAC

Safety: Tables					
No.	Population	IDS / Example Shell	Title	Programming Notes	Deliverable [Priority]
3.39.	Safety	LB17	Summary of Worst-Case Haematology Results by PCI Criteria Post-Baseline Relative to Baseline for Induction Phase	Rationale: ICH E3 and disclosure	SAC
3.40.	Safety ETP	LB17	Summary of Worst-Case Haematology Results by PCI Criteria Post-Baseline Relative to Baseline for Extended Treatment Phase	Rationale: ICH E3 Footnote: "Note: Induction phase baseline used"	SAC
3.41.	Safety OL I	LB17	Summary of Worst-Case Haematology Results by PCI Criteria Post-Baseline Relative to Baseline for Open Label Induction Phase	Rationale: ICH E3 Footnote: "Note: Induction phase baseline used"	SAC
3.42.	Safety OL ETP	LB17	Summary of Worst-Case Haematology Results by PCI Criteria Post-Baseline Relative to Baseline for Open Label Extended Treatment Phase	Rationale: ICH E3 Footnote: "Note: Induction phase baseline used"	SAC
Laboratory: Urinalysis					
3.43.	Safety	UR1	Summary of Worst-Case Urinalysis Results by PCI Criteria Post-Baseline Relative to Baseline for Induction Phase	ICH E3	SAC

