### 15.12.9. Pharmacokinetic Tables

Pharmacokinetic: Tables					
No.	Population	IDSL / Example Shell	Title	Programming Notes	Deliverable [Priority]
PK concentration					
4.1.	PK	PKCT1	Summary of Plasma GSK2831781 Concentration-Time Data (ng/mL) for Induction Phase	Note: LLQ=10 ng/mL. SE and 95% CI (Lower, Upper) are set to missing if No. Imputed/n > 0.3.	SAC
4.2.	PK_ETP	PKCT1	Summary of Plasma GSK2831781 Concentration-Time Data (ng/mL) in Extended Treatment Phase	Note: LLQ=10 ng/mL. SE and 95% CI (Lower, Upper) are set to missing if No. Imputed/n > 0.3. Programming note: data should be summarised by dose group of Induction Phase	SAC
4.3.	PK_OL	PKCT1	Summary of Plasma GSK2831781 Concentration-Time Data (ng/mL) in Open Label Induction Phase by Double Blind Induction Treatment	Note: LLQ=10 ng/mL. SE and 95% CI (Lower, Upper) are set to missing if No. Imputed/n > 0.3. Please add a note: "Note that subjects had different doses during the Induction Phase"	SAC
4.4.	PK_OL_ETP	PKCT1	Summary of Plasma GSK2831781 Concentration-Time Data (ng/mL) in Open Label Extended Treatment Phase by Double Blind Induction Treatment	Note: LLQ=10 ng/mL. SE and 95% CI (Lower, Upper) are set to missing if No. Imputed/n > 0.3.	SAC
PK derived parameters					
4.5.	PK_ETP	PK03	Summary of derived plasma GSK2831781 pharmacokinetic parameters in Extended Treatment Phase (SC dosing)		SAC

Pharmacokinetic: Tables					
No.	Population	IDSL / Example Shell	Title	Programming Notes	Deliverable [Priority]
4.6.	PK_ETP	PK05	Summary of log-transformed derived plasma GSK2831781 pharmacokinetic parameters in Extended Treatment Phase (SC dosing)		SAC

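### Open-label laboratory, vital-sign and ECG tables show no split by induction arm and use the original baseline, so changes that arose on placebo can appear under open-label 450 mg

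*SAP*

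**What the plan says.** **Baseline.** SAP 7 reports all safety endpoints by phase and adds: "All study phases will use the same pre-dose baseline". SAP 5.2 defines it: "The baseline value will be the latest pre-dose assessment with a non-missing value, including those from screening and unscheduled visits". That is normally the Day 1 pre-dose value. No baseline at entry to open-label (OL) treatment is defined.

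**Who enters OL.** Protocol 4.2 says that placebo participants "who have not responded by the Induction Assessment (Week 10) will have opportunity to access Open Label treatment with GSK2831781 450 mg IV". Protocol 4.3.3 gives the same IV regimen, starting at Week 12, to every Week 10 non-responder whatever the arm.

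**Populations and tables.** SAP 4.3 and 4.4 define the OL safety populations as everyone dosed in the phase, by treatment received. In SAP 15.12.7 the OL induction tables are:
- change from baseline: 3.29 (chemistry), 3.37 (haematology), 3.65 (vital signs);
- worst case: 3.33 (chemistry), 3.41 (haematology), 3.45 (urinalysis), 3.69 (vital signs);
- QTc: 3.57 and 3.61.

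The OL extended-treatment equivalents are 3.30, 3.34, 3.38, 3.42, 3.46, 3.58, 3.62, 3.66 and 3.70. None is titled or annotated by induction arm. The worst-case chemistry and haematology tables and the QTc tables carry the footnote "Note: Induction phase baseline used". By contrast, PK Table 4.3 (SAP 15.12.9) is specified "in Open Label Induction Phase by Double Blind Induction Treatment", and Table 4.4 is split in the same way.

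**Phase allocation.** Under SAP 15.3.1 a phase begins on "the Study Day that they receive their first dose for that study phase", and the OL Week 12 window opens at "Participant's first dose of OL". The Week 10 window closes the day before. The OL schedule in Protocol 1.3, footnote 1, says: "Unless specified otherwise, all samples will be taken prior to administration of study treatment".

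**Adverse events.** SAP 15.4.2.1 assigns each event to the phase in which it starts.

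**The concern.** A placebo crossover receives active drug for the first time at Week 12. A re-treated participant has by then had up to four doses of antibody. If both share one column and one pre-study baseline, the column answers no single question. For the crossover, a change from Day 1 mixes about 12 weeks of active colitis on placebo with whatever follows the first active dose.

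The distortion can run either way. A placebo-period deterioration can look like a drug finding. A new change on drug can also be hidden if the value had moved in the opposite direction on placebo. Where the groups are pooled, an effect confined to first exposure is diluted by the re-treated participants.

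Safety and tolerability in all trial phases is a stated objective in both documents. After termination the SAP dropped the OL efficacy summaries but kept the tables listed above as final deliverables, so they will be produced.

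**Working it through.** The plan states no figure on this point. The check is a tracing of rules, followed by a sizing.

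**1. Age of the baseline.** The first OL dose is at Day 85. 85 - 1 = 84 days = 12 weeks. For a placebo crossover none of that time is on active drug.

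**2. Where the OL Week 12 sample goes.** Haematology, chemistry and urinalysis are scheduled at OL Week 12 and taken pre-dose. The Week 10 window ends the previous day and the OL Week 12 window starts on the dosing day, so the sample can only fall in the OL phase. SAP 15.3.1 then uses all observations for worst-case safety outputs. SAP 15.4.3 takes clock time into account for adverse events where it is collected; no matching rule is given for laboratory samples. The scheduled OL Week 12 ECG differs: footnote 9 of the OL schedule places it in the post-dose monitoring period. For ECG, only the age of the baseline is at issue.

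**3. Example.** A placebo participant's haemoglobin falls from 120 to 92 g/L by the pre-dose OL Week 12 sample. SAP 15.8.1 flags values below 80 g/L or a fall of 25 from baseline. 92 is above 80, but 120 - 92 = 28 exceeds 25. The value is flagged in the OL phase solely because of the original baseline, before any active drug. Creatinine, QTc, blood pressure and heart rate also have change-from-baseline criteria (SAP 15.8.1, 15.8.3, 15.8.4). Albumin and CRP have absolute limits only. For those, the problem is the pre-dose sample being counted as an OL value, and the display relative to baseline depends on the shell.

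**4. Share of crossovers in the OL induction column.** Share = nP(1 - pP) / [nP(1 - pP) + nA(1 - pA)], where pP and pA are Week 10 clinical response rates on placebo and active. The documents do not give these rates. I assumed pP of 20-40%, pA from pP up to 60%, and that every non-responder is dosed in OL.

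Arm sizes are from Protocol 9.2.1: 40 and 20 at Interim Analysis 3, and 68, 42, 42, 42 and 48 in full. They are consistent: 242 - 60 = 182; 182/13 = 14; 40 + 28 = 68; 3 x 14 = 42; 20 + 28 = 48. Active total: 68 + 126 = 194.

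| Setting | pP, pA | Placebo-first | Active-first | Share |
|---|---|---|---|---|
| 40/20 | 30%, 30% | 14 | 28 | 33% |
| 40/20 | 30%, 40% | 14 | 24 | 37% |
| 40/20 | 20%, 60% | 16 | 16 | 50% |
| 242 | 30%, 30% | 33.6 | 135.8 | 20% |
| 242 | 30%, 40% | 33.6 | 116.4 | 22% |
| 242 | 20%, 60% | 38.4 | 77.6 | 33% |

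SAP 2.4 reports few participants on the three middle doses, so the 40/20 rows are nearer to the data that will be analysed.

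**5. Size of the misattribution.** Take 14 placebo-first and 24 active-first. Suppose a fraction q of the 14 already have a shifted value at OL Week 12 and nothing new occurs on OL drug. The pooled column shows 14q/38: 1.8%, 3.7% and 7.4% for q = 5%, 10% and 20%. Under the full plan (33.6q/150) it shows 1.1%, 2.2% and 4.5%. Split by arm and referred to an OL-entry baseline, the placebo-first column shows 0% new changes.

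**6. Dilution, a separate effect.** An event in 20% of first-exposed and 0% of re-treated participants would show as 20% x share, that is 6.7% to 10% at the 40/20 stage.

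**The case against.** The case on the other side has real weight.

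- **Adverse events.** A reader might infer that the OL adverse-event tables (3.4, 3.12, 3.16, 3.21) also count placebo-onset events as OL events. They do not: they use no baseline, and the onset rule keeps such events in the Induction Phase. Those tables appear to pool the two groups, so dilution can apply to them, but misattribution does not.
- **Pooling is not stated outright.** The single OL IV column is noted for the disposition tables (1.3 and 1.5), not for safety, and SAP 15.13 places the mock shells in a separate document. The inference rests on the population definitions, the titles, and the missing induction-arm instruction that the PK tables do have. That is good evidence, not proof.
- **Tracing is possible.** A reader might infer that the two groups cannot be told apart anywhere. The listings follow each participant through the phases in order of induction treatment. Listing 24 gives all laboratory data for anyone with a value of potential clinical importance. With 30 to 40 participants this is workable, but it does not correct the summary tables.
- **Disclosure and purpose.** The baseline is footnoted on several tables, safety is descriptive, and the primary safety phase is the randomised Induction Phase, which this point leaves untouched. For re-treated participants the original baseline is a reasonable cumulative view. None of this makes it a suitable sole reference for someone first exposed at Week 12.

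**Conclusion.** The point holds for the OL laboratory, urinalysis, vital-sign and ECG tables that refer to baseline. The single baseline and the Study Day allocation are explicit. Together they let placebo-period changes appear as OL findings, and let a placebo participant's unexposed Week 12 blood sample enter the OL worst-case summaries. That the two groups share a column is a strong inference, to be confirmed against the shells.

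On the assumed response rates, crossovers are about 33-50% of the OL induction column at the 40/20 stage and 20-33% under the full plan. The illustrative misattributed rates run from about 1% to 7%, depending on how many crossovers already carry a shifted value. These are not predictions: the documents give neither the response rates nor that fraction.

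The documents do not support reading this as a fault in the adverse-event attribution or in the primary safety comparison.

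**What to change.** 1. In SAP 7 and 15.12.7, show the OL induction and OL extended-treatment safety tables by double-blind induction treatment (placebo-first; active-first), as PK Tables 4.3 and 4.4 already do.
2. For placebo-first participants, add change and worst-case results against an OL-entry baseline: the last value before the first OL dose. For ECG, use the last ECG before that dose, because the scheduled OL Week 12 trace is post-dose. Keep the original baseline for active-first participants as the cumulative view. Give any total column on the original baseline only, so that it does not mix two references.
3. Amend SAP 15.3.1 so that pre-dose assessments on the first OL dosing day form the OL-entry baseline and are left out of the OL post-baseline worst-case summaries. The Week 10 window closes the day before, so the amendment should also say whether these values count towards the double-blind worst-case summaries. Otherwise an abnormal value on that day could appear in no worst-case table.

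The cost is smaller column counts, one more baseline variable and some reprogramming of windows and tables. All the data are already collected.
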